1.1. Introduction

As the population of persons living with HIV ages in the United States, lung cancer is now the leading cause of cancer death, with risk related to both increased tobacco use as well as independent risk associated with chronic HIV infection. Lung cancer screening with annual low-dose chest CT has been demonstrated to reduce lung cancer mortality by up to 20% in a subset of high-risk smokers, though potential longitudinal benefits may be greatly reduced in those with comorbid illness. While lung cancer screening is both feasible and likely highly beneficial in many persons living with HIV, there are limited prospective data and no HIV-specific guidelines to support tailored lung cancer screening decision making in this population, who are at higher risk for multimorbidity associated with aging. This study will bridge this significant knowledge gap through the iterative development and evaluation of tools to guide the shared decision making process for lung cancer screening in persons living with HIV. The study will consist of the following specific aims and approach: 1) Conduct a formative evaluation using qualitative methods to guide adaption and implementation of shared decision making for lung cancer screening tailored to persons living with HIV incorporating lung cancer risk as well as HIV severity, comorbidity and life expectancy; and 2) Pilot and evaluate tailored shared decision making using mixed-methods to assess the impact on patient knowledge and decisional conflict, as well as intervention acceptability, appropriateness and fidelity. Aim 1 includes focus groups of persons living with HIV and interviews with their primary providers to determine key barriers and facilitators to tailored shared decision making. Measures of comorbidity and life expectancy are also incorporated into this process to develop a tailored shared decision making intervention. Aim 2 is a single-arm feasibility trial to determine both the preliminary effectiveness and implementation of the shared decision making approach. The results of this study will be used to develop and refine tools for shared decision making for lung cancer screening in persons living with HIV, allowing for subsequent scale-up of implementation and assessment of effectiveness, reach and sustainability in a multicenter trial. This study directly addresses NIH high priority research topics of malignancy and comorbidity associated with HIV.

1.2. Relevant Literature and Data

1.2.1. The burden of lung cancer is particularly high in aging persons with HIV (PWH).

Non-AIDS defining cancers are increasing in aging PWH. Approximately 50% of PWH in the US are over the age of 50, and lung cancer is now the leading cause of cancer death.^{1,2} The cumulative incidence of lung cancer by age 65 in this population is 2.2% vs. 1.3% in the non-infected population.³ This is largely attributable to high rates of tobacco use in U.S. PWH; an estimated 60% are current or former smokers.⁴ There is also evidence for an increased risk of lung cancer independent of smoking.^{5,6} Among those who are diagnosed with lung cancer, PWH may also be less likely to receive appropriate treatment and have poorer survival than their uninfected counterparts, highlighting the potential benefits of early detection to overcome these disparities.⁷⁻⁹

1.2.2. LCS is an effective tool for early detection in high-risk populations. The National Lung Screening Trial (NLST) enrolled >50,000 current or former smokers (quit within 15 years) of ≥30 pack-years, aged 55-74, and randomized individuals to LDCT vs. chest radiograph. The LDCT arm had a 20% decrease in deaths from lung cancer and a 7% decrease in all-cause

mortality.¹⁰ The benefits of LCS have been confirmed in a subsequent trial,¹¹ and the United States Preventive Services Task Force (USPSTF) recommends screening for a similar high-risk group.¹² Due to this recommendation, and similar guidelines from the Centers for Medicare and Medicaid services (CMS), LCS is provided to insured eligible individuals without cost-sharing.¹³ This benefit is also extended to many who are age ≥ 50 with smoking history ≥ 20 pack-years with an additional lung cancer risk factor based on National Comprehensive Cancer Network (NCCN) guidelines.¹⁴

1.2.3. Lung cancer screening is feasible and likely beneficial in most eligible PWH. The NLST did not include PWH;¹⁰ however, several single-arm feasibility trials of PWH demonstrate similar outcomes.^{15,16} Our own group has demonstrated that false-positive findings and procedural complications do not appear to be more common in PWH with well-controlled HIV.^{17,18} Given the lack of feasibility of a large-scale trial, our group modified the Lung Cancer Policy Model used by USPSTF for PWH using best estimates from the literature for a number of parameters unique to PWH including non-lung cancer mortality rate by age and CD4 strata and found that lung-cancer specific mortality reduction using standard eligibility criteria was 18.9% for PWH who are adherent to ART, similar to the 20.0% seen in NLST¹⁹ (see preliminary work). Thus, LCS is likely to benefit PWH using similar criteria as the general population.

1.2.4. However, LCS may be less effective in persons with a high burden of comorbidity and competing health risks. To minimize harms and maximize benefits, patients who have conditions that substantially limit life expectancy or the ability to have lung surgery should not undergo LCS per USPSTF guidelines.¹² Evaluating comorbidities and accounting for competing risk of death from other causes is crucial in assessing the effect of LCS on mortality.²⁰ Aggregate benefits of screening may not be experienced for several years after cancer diagnosis (“pay-off” time).²¹⁻²³ Unfortunately, those at the highest risk for lung cancer may also be at the highest risk from related diagnostic or therapeutic complications, and/or competing causes of death, and thus unlikely to have sufficient “pay-off” time to derive benefits of screening.^{24,25} Indeed, patients who met NLST criteria but had higher Charlson Comorbidity Index (CCI) scores (≥ 2 vs 0-1) showed significantly lower 5-year survival among patients with resectable stage I non-small cell lung cancer.²⁶

1.2.5. Shared decision making (SDM) is used to guide patient-centered decisions regarding LCS; however, there are no tools tailored for PWH. SDM is defined as an “approach where clinicians and patients share the best available evidence when faced with the task of making decisions, and where patients are supported to consider options to achieve informed preferences.”^{27,28} SDM is particularly important for LCS given comorbidities and competing risks in the eligible target population,²⁹ and is mandated by CMS and recommended by other guidelines.¹³ Several tools, or decision aids, have been evaluated to guide and personalize SDM, but most focus on individual risk assessment of lung cancer rather than assessment for individualized competing risks or harms. While we do not intend that distinct thresholds for comorbidity or life-expectancy should definitively guide SDM, almost all guidelines recommend considering these elements in SDM. In those who have lower life expectancy, screening may be approached as more patient preference-sensitive.^{12,29} Thus, an understanding of competing risk and life expectancy may be beneficial for clinicians and patients in deciding whether to screen, and particularly for PWH given their burden of multimorbidity.²⁵

1.3. Compliance Statement

This study will be conducted with Fred Hutchinson Cancer Center (FHCC) policies and procedures and all applicable Federal and state laws and regulations including 45 CFR 46 and the HIPAA Privacy Rule. Any episode of noncompliance will be documented. Collecting,

recording, and reporting of data will be accurate and will ensure the privacy, health and welfare of research subjects during and after the study.

2. Study Objectives

2.1. Aims

Aim 1. Conduct a formative evaluation using qualitative methods to guide adaption and implementation of shared decision making (SDM) for LCS tailored to PWH incorporating lung cancer risk as well as HIV severity, comorbidity and life expectancy.

H1. Key themes will emerge from focus groups and interviews with PWH and providers that will help structure a SDM process for PWH and determine how best to incorporate measures of HIV severity, comorbidity and life expectancy, such as the Veterans Affairs Aging Cohort Study and Charlson Comorbidity risk indices.

Aim 2. Pilot and evaluate tailored SDM using mixed-methods to assess the impact on patient knowledge and decisional conflict, as well as intervention acceptability, appropriateness and fidelity.

H2. Tailored SDM will result in improvements in patient knowledge and result in low levels of decisional conflict. Surveys of patients and interviews of patients and stakeholders will be utilized to inform and subsequently iterate the intervention with regards to acceptability, appropriateness and fidelity.

2.2. General Schema of Study Design

The study will include: 1) a multilevel qualitative assessment of PWH and their providers to gather formative information to guide implementation of SDM for LCS and 2) A pilot SDM program tailored for PWH with a mixed-methods assessment.

2.3. Study Duration, Enrollment and Number of Sites

2.3.1. Date Range of Study

This study will be conducted October 2020-September 2022. Estimate to complete Aim 1 in months 1-10 and Aim 2 in months 11-24.

2.3.2. Total Number of Study Sites/Total Number of Subjects Projected

There will be two sites for the study which perform separate tasks. The FHCRC will serve as the administrative home for the project and house the study Co-leader ([name]) and the research coordinator. Will also be site of all data analysis.

The UW Madison Clinic will serve as the enrollment site and clinical visit site for Aim 1. UW Madison Clinic will serve as the enrollment site and both UW Madison Clinic and Fred Hutchinson Cancer Center will serve as the clinical visit sites for Aim 2. In Aim 1, Madison Clinic conference space will supplement online focus groups and interviews. In Aim 2, data collection will be concurrent with a clinical visit for LCS enrollment.

2.4. Study Population

2.4.1. Inclusion Criteria

Aim 1. We will recruit participants from two groups: PWH enrolled in the local UW HIV cohort and primary providers at Madison Clinic and other Seattle-based clinics serving PWH. Using proposed USPSTF guidelines, participants enrolled in the registry who are current or former smokers, ≥ 50 years old, and report ≥ 20 pack-years smoking history (n=165) will be eligible for recruitment. A purposive sample will be recruited, making every effort to include patients of diverse race/ethnicity, sex, income, and spanning the eligible age range for LCS. We will pay particular attention to recruiting women as well as men. Clinicians (medical doctors, physicians assistants, and nurse practitioners) who provide primary care for PWH (n=48) will be eligible.

Aim 2:

PWH who are eligible for LCS based on current USPSTF criteria^[SMA1]. Plan to enroll approximately 50% who have never had a lung cancer screening exam, and 50% who are overdue (~12 months) for lung cancer screening exam.

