3.2.2. Shared Decision Making visit

The coordinator will administer a pre-SDM survey that includes participant demographics, participant-reported risk factors, tobacco history, an assessment of LCS knowledge (the LKS) used in our prior study³⁶ and minimalist/maximalist approach to healthcare⁴⁰ (Addendum 8.1). Participants will then meet with the LCS nurse practitioner (NP), who will provide the SDM intervention and will supplement the discussion using language regarding comorbidity and life expectancy developed in Aim 1 to frame decisions; they will come to a mutual decision on whether to move forward with the screening process. To inform the tailored discussion, comorbidity burden and life expectancy will be estimated for each participant prior to the visit, using data from the UW HIV Information System (UWHIS) and EPIC to generate CCI, LCRAT, LCDRAT and VACS 2.0 Index from electronic-health records data (ICD-10 codes and most recent lab values within 1 year). A HIPAA waiver has been requested for this purpose. Prior to the visit, the participants lung cancer risk will be calculated using the LCRAT and the LCDRAT tools and mortality risk will be calculated using the VACS Index 2.0. The NP will receive an interpretation of these results, based on published literature and our preliminary work to guide discussion. The NP will complete SDM with the patient using the tailored SDM tool (Addendum 19) and guide (Addendum 20). The coordinator will observe the SDM discussions in order to complete an observational checklist assessing fidelity of the intervention (Addendum 9). Participants will then complete a post-SDM survey re-assessing LCS knowledge, resultant decisional conflict using the low literacy decisional conflict scale,³⁷ as well as validated quantitative 4-item scales of acceptability and appropriateness developed by Co-I [name], the Acceptability of Intervention Measure (AIM) and the Intervention Appropriateness Measure (IAM)(Addendum 8.2)³⁸ Participants who go on to LCS will be enrolled in the LCS program and linked to screening by a patient navigator.

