3.2.5. Sample Size

As this is a feasibility study and the majority of our outcomes are summarized, there is no appropriate power calculation to determine sample size. In our previous study of pre- and post-SDM knowledge, we found an improvement in overall understanding of possible harms of lung cancer screening from 69% to 93% in a group of 45 patients ($p=0.002$), and relatively few patients would need to be enrolled to demonstrate that magnitude of change. However, because we are interested in a robust sample to assess the other outcomes, we plan to enroll at least 50 patients into the SDM intervention. We will then sample patients for interviews until thematic saturation on acceptability and appropriateness are reached.

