3.2.6. Data Collection and Analysis

Pre-/post-SDM survey data will be collected via tablet, with a paper option if desired. Participants will directly enter data into secure Research Electronic Data Capture (REDCap, Vanderbilt University) software. All interviews will be recorded and transcribed. Key outcomes are described above. Pre- and post-intervention LKS responses will be compared via Chochran-Mantel-Haenszel or Friedman test based on data type. A Chochran-Mantel-Haenszel test will be used with categorical data and a Friedman test will be used with non-categorical data. The DCS will be summarized as the median of scores for participants from 0 (extreme certainty) to 100 (extreme uncertainty). The IAM and AIM will also be summarized and presented as range of scores from 1 (low acceptability/appropriateness) to 5 (high acceptability/appropriateness). Fidelity will be summarized as median percent of checklist items completed. Joint displays consistent with a mixed-methods convergent design will be used to analyze and interpret the data, with themes mapped onto the TICD as in Aim 1.³⁹

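### Should the Aim 2 results be broken down by screening history because enrolment is balanced on it?

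*Combined protocol and SAP*

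**What the plan says.** Section 2.4.1 of the protocol describes the intended Aim 2 mix: "Plan to enroll approximately 50% who have never had a lung cancer screening exam, and 50% who are overdue (~12 months". It gives no reason for the mix. Section 3.2.5 treats the sample as one group: "we plan to enroll at least 50 patients into the SDM intervention". It states that no power calculation is appropriate, because this is a feasibility study whose outcomes are mostly summarized.

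Section 3.2.6 holds the analyses. For knowledge: "Pre- and post-intervention LKS responses will be compared via Chochran-Mantel-Haenszel or Friedman test based on data type". For decisional conflict: "The DCS will be summarized as the median of scores for participants". For acceptability and appropriateness: "The IAM and AIM will also be summarized and presented as range of scores". Screening history appears in none of them, and breakdowns are neither named nor excluded.

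The hypothesis for Aim 2, in section 2.1, reads: "Tailored SDM will result in improvements in patient knowledge and result in low levels of decisional conflict". It makes no distinction by screening history.

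**The concern.** Screening history is the only participant characteristic for which Aim 2 sets a target proportion. When a study controls its mix on a variable, one expects to see results by that variable, and here there are none. People who have been screened before may know more at the start and have less to gain. A pooled gain would then be an average of two different gains, weighted by a mix that the investigators chose, and it would understate the gain in the never-screened.

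The results are also meant to refine the tool, "allowing for subsequent scale-up of implementation and assessment of effectiveness, reach and sustainability in a multicenter trial". A clinic with a different mix could not carry the pooled figure over without knowing whether it holds in both groups. The description of the survey adds to the impression. Section 3.2.2 lists a "pre-SDM survey that includes participant demographics, participant-reported risk factors, tobacco history, an assessment of LCS knowledge", and prior screening is not among the items named. That last point carries no weight: the survey itself is in an addendum that is not in the public document, and nobody can recruit to this mix without knowing each person's screening history.

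**Working it through.** **1. The question asked and the analysis planned.** Section 2.1 predicts better knowledge and low decisional conflict in people who receive the intervention. Section 3.2.6 compares each participant's knowledge before and after the visit and summarizes the scores of the whole sample. Each participant is his or her own control, so the mix cannot bias the comparison for the people enrolled. It only determines which average is estimated. No aim, hypothesis or sample-size statement asks for a contrast between never-screened and overdue participants.

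**2. The only effect size in the plan.** Section 3.2.5 cites a rise from 69% to 93% in 45 patients, p=0.002. That is 31/45 = 68.9% and 42/45 = 93.3%, a net change of 11 patients. The discordant counts are not given. With 12 improving and 1 worsening (assumed), McNemar's statistic is (12 − 1)²/13 = 9.31, p = 0.0023, which agrees with the stated value. I therefore take c = 1/45 as the share who worsen. The figure is for understanding of harms only, in patients whose screening history is not stated.

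**3. How far the mix moves the pooled gain.** Assume that the never-screened go from 69% to 93% (a gain of 24 points) and that the overdue also end at 93%. With never-screened share s,

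pooled gain = s × 24 + (1 − s) × (93 − overdue baseline).

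The 95% half-width for a paired change g is 1.96 × √[(b + c − (b − c)²)/n], with b = g + c. At n = 50:

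| Overdue baseline (assumed) | Pooled gain, s = 0.5 | s = 0.4 to 0.6 | Shift either way | Half-width, n = 50 |
|---|---|---|---|---|
| 69% | 24.0 | 24.0 to 24.0 | 0 | 13.2 |
| 80% | 18.5 | 17.4 to 19.6 | 1.1 | 12.2 |
| 85% | 16.0 | 14.4 to 17.6 | 1.6 | 11.7 |
| 90% | 13.5 | 11.4 to 15.6 | 2.1 | 11.1 |

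Example, last row: b = 0.135 + 0.022 = 0.157; 1.96 × √[(0.1794 − 0.0182)/50] = 0.111. The sampling error is at least five times the effect of the mix (11.1/2.1 = 5.3).

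**4. What a split table could show.** With 25 per group, the half-width for the difference in gain is 1.96 × √[(V₁ + V₂)/25], where V = b + c − (b − c)² in each group. For the never-screened, V₁ = 0.2268.

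| Overdue baseline (assumed) | True difference in gain | V₂ | Half-width | Chance that the 95% interval excludes zero |
|---|---|---|---|---|
| 80% | 11 | 0.1575 | 24.3 | 14% |
| 85% | 16 | 0.1180 | 23.0 | 28% |
| 90% | 21 | 0.0735 | 21.5 | 48% |

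The last column is the normal approximation, Φ(d/SE − 1.96) + Φ(−d/SE − 1.96), with SE = half-width/1.96. In every row the assumed difference lies inside the half-width. Within one group of 25, the half-width for a 24-point gain is 18.7 points.

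**The case for a change.** The strongest case for a breakdown does not depend on any assumed baseline. One pooled figure cannot distinguish a uniform gain from a gain concentrated in half the sample. Gains of 33 and 15 points pool to 24, and so do 43 and 5. In the second case, a never-screened share running from 40% to 70% would move the pooled gain from 20.2 to 31.6 points, and a split table would probably reveal the 38-point difference (half-width 24.2 at 25 per group). The cost is one sentence and one table, no tests are needed, and stating the breakdown in advance would prevent it from being shown only when it looks interesting. Nor does naming the Cochran-Mantel-Haenszel test answer the point: in a pre/post comparison the stratum is normally the participant, and section 3.2.6 does not define strata by screening history.

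Part of this stands. Section 3.2.6 names no breakdown, a pooled value can conceal a difference, and a descriptive table would be informative. But the large difference that the table could detect is assumed: the documents give no knowledge data by screening history. For 33 against 15 the half-width is 25.9 points against a difference of 18, so the table would again leave the matter open. A pooled mean that averages over unequal subgroups is a feature of any mixed sample. Recruiting for diversity does not oblige a single-arm feasibility study to report by every characteristic it recruits on. Since the plan does not limit reporting to the pooled group, the table can be added when results are written up without contradicting anything.

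**Conclusion.** The concern does not hold. The observation is accurate: the mix is set in section 2.4.1 and does not return in section 3.2.6. But the planned analyses answer the hypothesis in section 2.1, which concerns the whole sample, and they are valid for it at any mix. Under assumed overdue baselines of 80% to 90%, a 10-percentage-point departure from the even split moves the pooled gain by 1.1 to 2.1 points, against a sampling half-width of 11.1 to 12.2. In the same cases a split at 25 per group would have between-group half-widths of 21.5 to 24.3 points for differences of 11 to 21.

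These figures rest on assumptions: the baselines by screening history, a common end point of 93%, one binary knowledge item standing in for the scale, and 1 in 45 worsening. A much larger difference would change the arithmetic in steps 3 and 4, but not the fact that no objective calls for the comparison. Reporting the achieved mix and descriptive results by group is a matter of preference. Its absence alters no planned result or conclusion.

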2.4.2. Exclusion Criteria

Those found to be ineligible for LCS on coordinator review; or who are non-English speaking or have cognitive dysfunction that would prevent participation in SDM.

3. Study Procedures

3.1. Aim 1

3.1.1. Recruitment, enrollment and consent

PWH who are recruited for focus groups will be identified through the research registry (in which they have consent for contact for any future studies). Participants will be recruited from the registry who meet the following criteria: current or former smokers, ≥ 50 years old, and report ≥ 20 pack-years smoking history (n=165). The research coordinator (RC) will contact potential participants and confirm eligibility. An initial telephone script (Addendum 1) will be used to contact and briefly explain the study. Verbal consent (Addendum 2.1, Addendum 2.2) will be used prior to the focus groups. Participant clinicians will be recruited by Madison clinic provider [name] with the assistance of the RC. Participant clinicians will also complete an electronic consent prior to the interviews (Addendum 2.3). An informational flyer will also be posted at UW Madison Clinic (Addendum 15.1) throughout Aim 1 enrollment.

